7.5 Duration of therapy

In the absence of treatment delays due to AEs, the treatment will continue up to 3 years or until disease progression, death of patient for any cause or meeting the treatment discontinuation criteria, whichever comes first.

7.6 Study Discontinuation

Patient will stop receiving the study treatment if any of the following criteria are met:

1) Disease progression

Disease progression is defined as rapid growth of multiple measurable, non-measurable, or new lesions, or at least a 20% increase in the sum of diameters of target (measurable) lesions, taking as reference the smallest sum on study (this includes the baseline sum if that is the smallest on study). In addition to the relative increase of 20%, the sum must also demonstrate an absolute increase of at least 5 mm. (Note: the appearance of one or more new lesions is also considered progression).

2) Noncompliance

If the patient is not able to be compliant with the treatment schedule in the absence of toxicity, missing medications by non-medical reasons that are reported to the research staff more than 14 days, the study treatment should be discontinued for the patient.

3) Sustained toxic effects

Study treatment will be discontinued for patients who have sustained toxic effects that are attributed to the study drug and require a dose interruption lasting more than 8 weeks.

4) Initiation of new anticancer treatment

In patients for whom the investigator, in his or her judgment, determines new treatment for breast cancer is warranted, the study treatment may be discontinued.

5) Patient withdraws consent

Patients have the right to voluntarily withdraw from the study at any time for any reason. Every effort should be made to obtain information on patients who withdraw from the study. The primary reason for withdrawal from the study should be documented on the appropriate Case Report Form (CRF) in the RedCap database. However, patients will not be followed for any reason after consent has been withdrawn

6) Any medical condition that the investigator, IND medical monitor or Novartis and PUMA determines may jeopardize the patient's safety if he or she continues in the study

7) Intolerable toxicity related to study treatment determined by the investigator to be unacceptable given the individual patient's potential response to therapy and severity of the event

- 8) Pregnancy
- 9) Symptomatic deterioration attributed to disease progression

7.7 Follow up

Patients will be followed for safety for 30 days following the last dose of study drug, or until receipt of another anticancer therapy, whichever comes first.

Patients who have an ongoing major study treatment related AE upon study completion or at discontinuation from the study will be followed up to 6 weeks until the event has resolved to baseline grade, the event is assessed by the investigator as stable, new anticancer treatment is initiated, the patient is lost to follow-up, the patient withdraws consent, or until it has been determined that study treatment or participation is not the cause of the AE.

After treatment discontinuation, information on survival follow-up and new anti-cancer therapy will be collected via telephone calls, patient medical records, and/or clinic visits approximately every 6 months for 2 years (unless the patient withdraws consent or study is terminated).

7.8 End of Study

The end of this study is defined as the date when the last patient, last visit (LPLV) occurs or the date at which the last data point required for statistical analysis (i.e., OS) or safety follow-up is received from the last patient, whichever occurs later. LPLV is expected to occur 3 years after the first patient is enrolled.

7.9 Correlative Research

Blood: Research blood, approximately 30 ml, will be collected at baseline and then every 2 cycles until the end of study treatment. Each blood collection will consist of 1x10mL red top tube (for serum) and 2x10mL EDTA tubes (for plasma and PBMC isolation). Samples will be processed and aliquots banked in the MDA IBC translational lab for future research. Samples will be stored in the short term at -80C (serum and plasma, Z12.4041) and LN2 dewar (for PBMCs) in the Zayed laboratory and transferred to off-site storage at Cryogene per routine laboratory procedures. Samples will be coded by a de-identification number and a key will be maintained by the research staff to associate each sample with the related clinical data. For any visits performed outside of MD Anderson, research blood will not be collected.

Tissue: Fresh tissue samples from breast/chest wall, or a metastatic site including lung, liver or lytic lesions of the bone that may be safely accessed, will be collected via image-guided core biopsy. Tissue should be from a viable section of the tumor. Core needle biopsy specimen diameter should not be smaller than 16 gauge with 2 or more cores preferred. Viable tumor resection biopsies should not be less than 25 mg. Fine needle aspirates are not acceptable. Samples will be collected using a Celcuity provided specimen collection kit and then delivered directly to Celcuity's CLIA-certified and CAP-accredited laboratory where the CELsignia MP test (HER2, EGFR, HER3, c-MET etc.) is performed. Additional details regarding sample collection and processing are included in Appendix 2, "CELsignia Collection Kit User Instructions Card". Please also see Appendix 3 for the "CELsignia Specimen Collection Requisition" form.

In addition to the CELsignia MP test, remaining tissue will be banked in the MDA IBC Lab for future research and to perform companion genomic testing to include major relevant pathways affected by the combination treatment. A total of 4-6 cores will be obtained from each patient, 2-4 of which will be sent to Celcuity for the CELsignia assay. The remaining cores will be preserved in OCT in order to preserve morphology, for further research on biomarkers of response/resistance to the therapy. IHC for c-MET will not be used for patient selection for the clinical trial given lack of validated clinical data.

Future studies performed on tissue and/or blood may include, but will not be limited to analysis of genomics, RNA, protein expression, or other analytes to study biomarkers, mechanisms of action, mechanisms of response/resistance, and pathways of interest.

In addition, we will perform mandatory collection of available data on cancer genomics that has been performed on the cancers of study participants for purposes outside of this study.

7.10. Study Calendar

Trial Period:	Screening Phase	Treatment Cycles 1 cycle=28 days ^a							End of Treatment	Post-Treatment	
		1	2	3	4	5	6	7		Safety F/U ^f	F/U ^g
Scheduling Window (Days):	Screening /Baseline Within 28 days +/- 3 days	1 ± 3	2 ± 3	3 ± 3	4 ± 3	5 ± 3	6 ± 3	7 ± 3	8+ ± 3		1 month 2 years
<hr/>											
Informed Consent	X										
Inclusion/Exclusion Criteria	X										
Physical Exam ^b , V/S, concomitant medications, ECOG ^b	X	X	X	X	X	X	X	X	X ¹		
Adverse Events ^b	X	X	X	X	X	X	X	X	X ¹	X	X
Pregnancy Test – Urine or Serum β-HCG (for women with childbearing potential)	X	X	X	X	X	X	X	X	X ¹		
CBC and Biochemical Profiles ^c	X	X	X	X	X	X	X	X	X ¹		
Urine analysis ^c	X	X	X	X	X	X	X	X	X ¹		
EKG, MUGA or ECHO as SOC ⁱ	X			X			X				
Radiological Evaluation as clinically indicated and as SOC ^d	X		X		X		X		X ¹		
Correlative Studies Blood Collection ^e	X		X		X		X				
Biopsy ^h	X										
Survival Status											X
Neratinib ^j		X	X	X	X	X	X	X			
Capmatinib ^j		X	X	X	X	X	X	X			
Endocrine Therapy ^K		X	X	X	X	X	X	X	X		

- a. Study treatment can be up to 3 years until the treatment is discontinued.
- b. Complete physical exam during the screening period. This will not be repeated if done within 8 (+/- 3 days) days before the start of treatment. During treatment Physical Exam as clinically indicated prior to trial treatment administration. Adverse events and ECOG performance status assessment can be done within 8 (+/- 3 days) days before the start of treatment. If a virtual visit is required, then physical exam and VS will not be obtained.
- c. Hematologic and biochemical profiles (CBC, albumin, alkaline phosphatase, ALT, AST, LDH, amylase, lipase, uric acid, calcium, glucose, phosphorus, potassium, sodium, magnesium, total bilirubin, total protein, BUN, creatinine, as standard of care (will not be repeated if done within 8 (+/- 3 days) days before the start of treatment). During treatment, an earlier evaluation will be performed if clinically indicated.
- d. Radiological evaluation will be performed every 2 cycles as standard of care and may include CT of the chest and abdomen, Ultrasound, bone Scan and X-Rays, brain MRI as clinically indicated for standard of care. PET/CT, Chest wall/breast photos may also be performed as indicated for standard of care. During treatment, an earlier evaluation will be performed if clinically indicated. The same method of evaluation, specific to the subject's condition, will be performed according to the time points.
- e. Blood (EDTA tube) and serum (red tube) for correlative studies. Approximately 30cc of blood will be drawn at baseline, and every 2 cycles (i.e. 3th, 5th, 7th, etc.). For any visits performed outside of MD Anderson, research blood will not be collected. Correlative research blood is mandatory.
- f. The Safety Follow-Up Visit should be conducted approximately 30 days after the last dose of trial treatment or before the initiation of a new anti-cancer treatment, whichever comes first. All AEs that occur prior to the Safety Follow-Up Visit should be recorded. Safety Follow-Up Visit can be done in the clinic, or by phone/video if patient is not willing to come to the clinic for follow up.
- g. 2 years follow up can be performed every 6 months in the clinic, or by phone/video if patient is not willing to come to the clinic for follow up.
- h. Mandatory to Phase II patients only. Biopsy at baseline can be combined with the primary diagnosis biopsy, or any time before the initiation of this trial to confirm the Celculty assay score.
- i. EKG, MUGA or ECHO will be performed every 3 cycles as standard of care.
- j. Participants may follow Study Medication Disposal Guide of MDA to dispose of study medications locally when participants cannot come back to study site to return remaining study medications and medication bottles. Participants may also capture pictures of the pill diaries and send them to research staff, if needed.
- k. ER+ breast cancer patients only (defined at ER $\geq 10\%$) will receive continuous aromatase inhibitor therapy (of physician's choice) by mouth dosed once daily. In addition, for pre-/peri-menopausal women with ER+ breast cancer, ovarian suppression therapy will also be administered.
- l. If applicable; can be combined with post 1 month follow up.

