7.2 Dosing level and Drug Administration

All participants will receive two drugs (neratinib and capmatinib) during the study as scheduled per Schema. Capmatinib and neratinib will be provided by Novartis and Puma respectively, and not billed to the patient. Additionally, patients with ER+ breast cancer will receive endocrine therapy (AI +/- ovarian suppression). Endocrine therapy is standard of care (SOC), not provided by the study.

The Phase Ib portion of the trial will determine the Maximum Tolerated Dose (MTD) from the combination of dosing levels listed in Tables 2 and 3, starting at Dose Level (1,1) (capmatinib PO 400 mg twice per day and neratinib PO 120 mg on days 1-7, then 160 mg through end of treatment). The maximum accrual for phase Ib is 18 patients (including the possibility of adding up to 6 additional ER+/HER2 negative patients in a safety assessment of aromatase inhibitor treatment).

The Phase II portion of the trial will enroll 29 patients treated at the MTD determined from the phase Ib portion of the study.

Total accrual of this study will be up to 47 patients

Both drugs are oral agents and each study cycle will be 28 days.

Patient will take study drugs by mouth with or without food per cohort dosing. Neratinib will be taken once daily with food. Capmatinib will be taken twice daily about 12 hours apart (+/-2 hours) with or without food. Patients will have a medication diary to record daily study drug intake information for each cycle. The study manager will collect it at each clinic visit as source document.

Neratinib

Neratinib will be supplied as 40 mg tablets, equivalent to 48.31 mg neratinib maleate. Tablets are film-coated, red, oval shaped and debossed with 'W104' on one side and plain on the other side. 3 – 6 tablets daily will be prescribed based on patient's dose level. Tablets should be swallowed whole (tablets should not be chewed, crushed, or split prior to swallowing).

If a patient misses a dose, it should not be replaced, and the patient should be instructed to resume neratinib with the next scheduled daily dose.

Neratinib should be stored at controlled room temperature, 20°C to 25°C (68°F to 77°F); excursions permitted to 15°C to 30°C (59°F to 86°F).

Capmatinib

Capmatinib will be supplied at 200 mg and 150 mg tablets. Capmatinib should be taken twice daily with or without food. Tablets should be swallowed whole. Do not break, crush or chew the tablets.

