7.4 Dose Limiting Toxicity (DLT)

DLT is defined as any of the following possibly, probably, or definitely due to study therapy, assessed during the first 2 cycles [56 days]:

- Any death not clearly due to the underlying disease or extraneous causes
- Non- hematologic toxicity
 - Grade 3 or higher non-hematologic toxicity, Grade 3 diarrhea will be considered a DLT only if it lasts \geq 2 days despite prophylaxis and optimal standard medication and medical management.

- Grade 2 diarrhea lasting \geq 5 days despite prophylaxis and optimal standard medical management
- Pulmonary toxicity
 - Any grade of pneumonitis or ILD confirmed not attributable to infection or another etiology.
- Hy's Law case, defined as a patient meeting all of the following criteria:
 - ALT or AST \geq 3 x Upper Limit of Normal (ULN)
 - Total bilirubin >2 x ULN
 - Little or no evidence of cholestasis (alkaline phosphatase <2 x ULN)
 - No other identified explanation for the injury (such as hepatitis A, B, C, or other viral hepatic injury, alcohol ingestion, congestive heart failure).
- Neutropenic fever, defined as per CTCAE version 5.0:
ANC $<1000/\text{mm}^3$ and a single temperature of >38.3 degrees C (101 degrees F) or a sustained temperature of $>=38$ degrees C (100.4 degrees F) for more than one hour.
- Hematologic toxicity
 - Grade 4 neutropenia or thrombocytopenia >7 days
 - Grade 3 thrombocytopenia with bleeding
 - Grade 4 anemia

The targeted maximum DLT rate is 25%, and we will enroll patients in cohorts of size 3.

Table 4. Capmatinib and Neratinib overlapping toxicities

SOC	Capmatinib toxicity (Ref: CDS)	Neratinib toxicity (Ref: USPI and SmPC)
Congenital, familial and genetic disorders	Embryo-Fetal Toxicity	Embryo-Fetal Toxicity
Gastrointestinal disorders	Diarrhoea	Diarrhoea
	Vomiting	Vomiting
	Nausea	Nausea
	Constipation	Abdominal pain*
	Amylase increased	Stomatitis**
	Lipase increased	Dyspepsia
	Acute pancreatitis	Abdominal distension
		Dry mouth

General disorders and administration site conditions	Fatigue ¹	Fatigue
	Weight decreased	Weight decreased
	Back pain	
	Oedema peripheral ²	
	Non-cardiac chest pain ³	
	Pyrexia ⁴	
Hepatobiliary disorders	Alanine aminotransferase increased	Alanine aminotransferase increased
	Aspartate aminotransferase increased	Aspartate aminotransferase increased
	Blood bilirubin increased	Blood bilirubin increased

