8.1.5. Adverse Events of Special Interest

- **Pulmonary Toxicity:**
Interstitial lung disease (ILD) or pneumonitis, a diffuse parenchymal lung disease, is a group of fibrotic lung disorders that affect the alveoli of the lung. In theory, neratinib may induce interstitial lung disease as this risk was identified for similar compound(class effect).
- **Cardiac Toxicity (Left Ventricular Ejection Fraction Decreased):**

Small-molecule TKIs have been shown to be associated with a certain degree of cardiovascular side effects that are often reversible. In theory, neratinib may decrease left ventricular ejection fraction (LVEF) as this risk was identified for similar compounds (class effect).

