Grade 3 ($> 2.0 - 5.0 \times \text{ULN}$ with signs or symptoms; $> 5.0 \times \text{ULN}$ and asymptomatic)	Omit the dose until resolved to \leq grade 2, then If resolved in ≤ 14 days, resume treatment at the same dose level

	If resolved in > 14 days, then ↓ 1 dose level
Grade 4 (> 5.0 x ULN with signs or symptoms)	Permanently discontinue participant from capmatinib treatment
CARDIAC	
Electrocardiogram QT corrected (QTc) interval prolonged	
Grade 1 (QTcF 450-480 ms)	Maintain dose level
Grade 2 (QTcF 481-500 ms)	Maintain dose level
Grade 3 (QTcF ≥ 501 ms on at least two separate ECGs)	Omit dose until resolved to ≤ grade 2, then: If resolved in ≤ 7 days, resume treatment at the same dose level If resolved in > 7 days, then ↓ 1 dose level
Grade 4 (QTcF ≥ 501 or > 60 ms change from baseline and Torsades de pointes or polymorphic ventricular tachycardia or signs/symptoms of serious arrhythmia)	Permanently discontinue participant from capmatinib treatment
GASTROINTESTINAL	
Pancreatitis	
Grade 2	Maintain dose level
Grade ≥ 3	Mandatory: Permanently discontinue participant from capmatinib treatment
Diarrhea**	
Grade 1 (despite appropriate anti-diarrheal medication)	Maintain dose level
Grade 2 (despite maximal anti-diarrheal medication)	Omit dose until resolved to ≤ grade 1, then maintain dose level. If diarrhea returns as ≥ grade 2, then omit dose until resolved to ≤ grade 1, then resume treatment at ↓ 1 dose level
Grade 3 or 4 (despite appropriate anti-diarrheal medication)	Omit dose until resolved to ≤ grade 1, then resume treatment at ↓ 1 dose level
Vomiting	
Grade 1 (despite appropriate anti-emetics)	Maintain dose level
Grade 2 (despite appropriate anti-emetics)	Omit dose until resolved to ≤ grade 1, then maintain dose level. If vomiting returns as ≥ grade 2, then omit dose until resolved to ≤ grade 1, then ↓ 1 dose level.
Grade 3 (despite appropriate anti-emetics)	Omit dose until resolved to ≤ grade 1, then ↓ 1 dose level
Grade 4 (despite appropriate anti-emetics)	Omit dose until resolved to ≤ grade 1, then ↓ 1 dose level
Nausea	
Grade 1 or 2 (despite appropriate anti-emetics)	Maintain dose level

Grade 3 (despite appropriate anti-emetics)	Omit dose until resolved to \leq grade 1, then \downarrow 1 dose level
SKIN AND SUBCUTANEOUS TISSUE DISORDERS	
Rash/photosensitivity***	
Grade 1	Maintain dose level
Grade 2	Maintain dose level

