13.1 Phase 1b Dose-Finding Design

We will employ the Bayesian optimal interval (BOIN) design (Liu and Yuan, 2015; Yuan et al., 2016) (24, 25), with the 3+3 design run-in, to find the MTD (see Appendix 1 for design parameters). The BOIN design is implemented in a simple way similar to the traditional 3+3 design, but is more flexible and possesses superior operating characteristics that are comparable to those of the more complex model-based designs, such as the continual reassessment method (CRM) (Zhou et al., 2018)(26).

The target toxicity rate for the MTD is $\phi = 0.25$ and the maximum sample size for dose escalation is 18. We will enroll and treat patients in cohorts of size 3. DLTs are defined in **Section 7.4** and only those DLTs that occur within **the first 2 cycles (56 days)** will be used for dose finding. As shown in Figure 2, the Boin design uses the following rule, optimized to minimize the probability of incorrect dose assignment, to guide dose escalation/de-escalation:

- if the observed DLT rate at the current dose is ≤ 0.197 , escalate the dose to the next higher dose level;
- if the observed DLT rate at the current dose is > 0.298 , de-escalate the dose to the next lower dose level;
- otherwise, stay at the current dose.

The 3+3 design run-in will be applied to override the above decision rule when the number of patients treated at the current dose is 3. That is, we will escalate the dose if 0/3 DLT, stay at the current dose if 1/3 DLT, and de-escalate the dose if $\geq 2/3$ DLTs. For the purpose of overdose control, doses j and higher levels will be eliminated from further examination if $\Pr(p_j > 0.25 | \text{data}) > 0.95$ and at least 3 evaluable patients have been treated at dose level j , where p_j is the true DLT rate of dose level $j, j = 1, \dots, 3$. This posterior probability is evaluated based on the beta-binomial model $y_j | p_j \sim \text{binomial}(p_j)$ with $p_j \sim \text{uniform}(0,1)$, where y_j is the number of patients experienced DLT at dose level j . When the lowest dose is eliminated, stop the trial for safety. The probability cutoff 0.95 is chosen to be consistent with the common practice that when the target DLT rate $\leq 1/6$, a dose with 2/3 patients experienced DLT is eliminated. The above dose escalation/de-escalation and elimination rule can be equivalently presented in Table 18, which will be used to conduct the trial.

The steps to implement the Boin design are described as follows:

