Duration of response (DOR) is defined as the period from the date of the first occurrence of a CR or PR until the first date that progressive disease or death is documented. Progression-Free survival (PFS) is defined as the time from treatment onset to either disease progression or death from any cause. 2 year overall survival (OS) is defined as the time from treatment onset to death over 2 years. For events that have not occurred by the time of data analysis, times will be censored at the last contact at which the patient was known to be progression-free for DOR and PFS, or the last time the patient was known to be alive for OS. DOR, PFS and OS will be summarized by the Kaplan-Meier method, including estimates of median and mean survival along with 95% CI.

IND Office Safety and Efficacy Stopping Rule Monitoring:

The Investigator is responsible for completing toxicity summary reports and submitting them to the IND office Medical Monitor for review. These should be submitted as follows:

- **Phase 1b Dose-Finding:**

- A toxicity summary will be submitted after the first 3 evaluable patients complete 2 cycles (56 days) of study treatment, and every 3 evaluable patients thereafter, prior to changing dose levels or moving to the study Phase II portion. IND Sponsor approval will be obtained after each submission, prior to enrolling additional subjects.

- **Phase II – Toxicity Monitoring:**

A toxicity summary will be submitted after every 6 evaluable subjects complete 2 cycles (56 days) of study treatment until enrollment is complete. Patients treated at the MTD in the phase I portion will be included for phase II toxicity monitoring evaluation.

- An additional toxicity summary will be submitted for the subjects with ER+ breast cancer treated at the MTD with AI therapy, after the first 3, and first 6 evaluable patients with ER+ breast cancer treated at the MTD with AI therapy complete 2 cycles (56 days) of study treatment. This toxicity summary may include patients with ER+/HER2- breast cancer treated at the MTD in phase 1b and phase 2. If ≥ 2 out of 3 or 6 patients with ER+ breast cancer experience a DLT at the MTD, the MTD may be decreased to a lower dose level and used for patients with ER+ HER2 negative breast cancer in phase 2.

- **Phase II – Efficacy Monitoring:**

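### No on-treatment EKG or LVEF assessment is nominally scheduled inside the 56-day DLT window, so silent cardiac DLTs may go uncounted in the phase Ib dose decisions

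*Combined protocol and SAP*

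**What the plan says.** **What counts.** Section 7.4 defines a DLT as one of a list of events at least possibly due to study therapy, "assessed during the first 2 cycles [56 days". The list includes "Grade 3 or higher non-hematologic toxicity, Grade 3 diarrhea will be considered a DLT only if it lasts" two days or more despite management. There is no exemption for cardiac findings. Section 13.1 adds that "only those DLTs that occur within the first 2 cycles (56 days) will be used for dose finding".

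**When the decision is taken.** Section 4.1 has the IND Office review the safety data once every patient in the cohort has finished the 56 days. Section 13.2 says: "A toxicity summary will be submitted after the first 3 evaluable patients complete 2 cycles (56 days) of study treatment", and then after every further three.

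**When the heart is assessed.** In the Section 7.10 calendar the EKG/MUGA/ECHO row is marked at screening, cycle 3 and cycle 6, with nothing under cycles 1 or 2. Footnote i reads: "EKG, MUGA or ECHO will be performed every 3 cycles as standard of care".

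**Why cardiac findings are in scope.** Table 15 in Section 10.5.2 grades QTc from the tracing alone: "Grade 3 (QTcF ≥ 501 ms on at least two separate ECGs". Section 8.1.5 lists falling ejection fraction as an event of special interest, stating that in theory "neratinib may decrease left ventricular ejection fraction (LVEF) as this risk was identified for similar compounds (class effect". For asymptomatic patients, Section 10.3 bases the decision to continue neratinib on the measured ejection fraction and its change from baseline.

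**The concern.** A silent QTc or LVEF event of Grade 3 or higher meets the DLT definition if related to treatment, but it becomes visible only when someone measures it. The plan schedules that measurement nominally after the counting window closes. A patient with such an event could therefore be recorded as DLT-free when the next cohort's dose is set.

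Any error of this kind lowers the observed DLT rate and so favours escalation. Cohorts are of 3 and the maximum is 18 patients, so single events move decisions. The MTD chosen this way is the dose carried into phase II. Toxicity monitoring there also looks at two cycles (Section 13.2), so it is not built to recover what phase Ib missed.

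**Working it through.** **1. Window.** Section 7.2 gives the cycle length: "Both drugs are oral agents and each study cycle will be 28 days". Two cycles are 2 × 28 = 56 days, which agrees with Sections 4.1, 7.4 and 13.1.

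**2. Date of the first on-treatment cardiac assessment.** The calendar gives a cycle number ± 3 days and does not say whether a column means the start or the end of the cycle. Day 1 of cycle k is 28(k − 1) + 1.

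| Reading | Nominal day | Allowed range |
|---|---|---|
| Cycle 3 mark, visit on day 1 | 28 × 2 + 1 = 57 | 54–60 |
| Cycle 3 mark, end of cycle 3 | 28 × 3 = 84 | 81–87 |
| Every 3 cycles, counted as footnote e counts every 2 cycles (3rd, 5th, 7th), giving cycle 4 day 1 | 28 × 3 + 1 = 85 | 82–88 |

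All three nominal dates fall after day 56. Only the first reading overlaps the window: 3 of its 7 allowed days (54, 55, 56) are inside and 4 (57 to 60) are outside. The row can also be read as any one of the listed tests, in which case LVEF might not be measured even then.

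**3. The plan's decision rule.** With target 0.25 and default alternatives 0.6 × 0.25 = 0.15 and 1.4 × 0.25 = 0.35, the BOIN boundaries are:

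- escalation: ln(0.85/0.75) / ln[(0.25 × 0.85)/(0.15 × 0.75)] = 0.1968
- de-escalation: ln(0.75/0.65) / ln[(0.35 × 0.75)/(0.25 × 0.65)] = 0.2984

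These match the stated 0.197 and 0.298. With the 3+3 run-in, the uniform prior and the 0.95 elimination cutoff, every column of Table 18 is reproduced.

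**4. Effect of one uncounted DLT on the Table 18 action.**

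| True count | Action | Recorded count | Action |
|---|---|---|---|
| 1/3 | stay | 0/3 | escalate |
| 2/6 | de-escalate | 1/6 | escalate |
| 1/6 | escalate | 0/6 | escalate |
| 3/6 | de-escalate | 2/6 | de-escalate |

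The first two rows change the action and the last two do not.

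**5. Illustrative size.** The documents give no share of DLTs that would be silent, so this is an assumption shown over a range. If a share f of DLTs is unseen at a dose with true rate 0.40, the observed rate is 0.40(1 − f), and P(0/3) = [1 − 0.40(1 − f)]³:

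- f = 0: 0.60³ = 0.216
- f = 10%: 0.64³ = 0.262
- f = 25%: 0.70³ = 0.343

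**The case against.** **Cannot be counted.** A reader might infer that silent cardiac DLTs cannot enter the dose decisions at all. The documents do not support that. On the day-1 reading, the visit allowance lets the cycle 3 test fall on days 54 to 56. Unscheduled testing is possible: Section 8.2.2 lists 12-lead ECG and cardiac assessment among the safety assessments (without times), Section 9.0 allows extra cardiac monitoring at the physician's discretion when QT-prolonging drugs are continued, and Section 10.3 calls for watching for signs of heart failure. What stands is that none of these is a scheduled measurement inside the window, and a silent event gives no clinical trigger for one. Footnotes c and d allow earlier laboratory and imaging evaluation if clinically indicated; footnote i has no such sentence.

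**Laboratory tests.** A reader might extend the point to laboratory DLTs, because on the day-1 reading the draw that follows cycle 2 is nominally day 57. That does not hold up. The day-29 draw is inside the window. The imaging and research-blood rows are marked at cycles 2, 4 and 6, which suggests that columns may mean the end of a cycle, and on that reading the cycle 2 draw falls nominally on day 56. Footnote c also provides for earlier draws.

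**Little evidence of risk.** Section 8.1.5 calls the LVEF risk theoretical. The adverse-reaction tables (Tables 4 to 7 and 9) list neither QTc prolongation nor LVEF decrease. Entry requires LVEF of at least 50% and excludes QTcF of 470 ms or more. Capmatinib, whose dose-modification table supplies the QTc grading, stays at 400 mg b.i.d. across levels 1 to 3. This limits any claim about size. It does not remove the mismatch, because DLTs are counted for the combination at each level.

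**Results may be in hand.** The review follows the last patient's day 56, so cycle 3 results may exist for patients who started earlier, and the IND Medical Monitor must approve each dose change. But Section 7.4 turns on when an event is assessed and Section 13.1 on when it occurs, so it is unclear whether a finding on day 57 counts. Nothing requires the result before filing.

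**Conclusion.** The point holds as a mismatch between a counted endpoint and its measurement schedule. Every plausible reading of the calendar puts the first on-treatment EKG or LVEF assessment nominally after day 56. Asymptomatic cardiac DLTs are therefore not scheduled to be detected in time to count, and a cohort summary can be filed before the results exist. This does not depend on how the calendar columns are read; only the length of the gap does (one day, or about four weeks).

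The direction of any bias is toward escalation. Its size is unknown. The rise in P(0/3) from 0.22 to between 0.26 and 0.34 rests on an assumed true rate of 0.40 and an assumed unseen share of 10% to 25%, neither of which the documents give for cardiac events. It shows sensitivity and is not an estimate. The conclusion is confined to cardiac findings. It should be settled before the dose decisions rely on these counts, but it does not by itself invalidate the BOIN design, whose boundaries reproduce correctly.

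**What to change.** For phase Ib, the sponsor should reconcile the Section 7.10 calendar and footnote i with Sections 4.1, 7.4 and 13.1. There are two ways to do this, and the exact cardiac schedule is for the sponsor to settle:

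- align the first planned on-treatment EKG/LVEF assessment with the end of the DLT window; or
- keep the visit where it is and state that results of the end-of-cycle-2 or pre-dose cycle 3 day 1 assessment count toward the DLT evaluation, including those obtained within the visit allowance after day 56.

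Under either, require those results in the cohort summary before the next dose is assigned. While editing, say whether a calendar column means the start or end of the cycle, and whether the row requires both an EKG and an LVEF measurement.

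**Cost.** This is protocol wording and at most one calendar mark. Each cohort decision may wait a few days (60 − 56 = 4 at most on the day-1 reading). Moving the mark earlier lengthens the gap to the cycle 6 assessment and departs from the three-cycle interval. Counting results after day 56 means restating the window consistently wherever it appears. The observed DLT rate may come out slightly higher.
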